### ***Veteran involvement and Characteristics***

This 4-site research project aims to implement and evaluate the CV toolkit designed to increase identification of CV risk among women Veterans, enhance patient/provider communication about CV risk, and increase women Veterans engagement and retention in relevant health services including referrals to key health programs. We will recruit adult women Veterans who visit their women's health provider at one of the four study sites if a CPRS CV risk template was activated from their primary care visit or they attended the Gateway to Healthy Living program. As long as the woman Veteran patient is also able to give informed consent to complete our protocol, she is eligible to participate. We expect to approach up to 200 women Veterans per site over the study period in order to achieve a minimum of 65 women participants in the survey/interviews for CV toolkit at each site. Our goal is to have 260 women total (minimum 65 per site across 4 sites) engaged in the project over the course of the study. Participation includes a brief survey at baseline and six-month post-baseline, and for a subset of women, a brief qualitative interview (approximately every third consented woman with a completed survey will be approached for an interview for a minimum of 20 patient interviews at a site). Women will be consented at the time of the survey and interviews. The women will also be consented to link their responses to their medical records at the time of the survey.

We will also use medical record data (CPRS template data and CDW data) to evaluate the roll-out of the intervention and the referral rates at all sites. This data will be evaluated for all women patients seen by the providers in the study over the study period. The data will only be evaluated in the aggregate and will not be linked to the patient survey or interview data (unless medical record access consent is received at the time of the survey).

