**Quantitative Analysis:** We will use descriptive and inferential statistics to understand variations in the measures described above. For patients, we will conduct bivariate analysis to examine variations in outcomes (CV risk factor control, cardiac event or procedure, etc.) by those who participated in the *Gateway to Healthy Living* program, versus those who received a referral to a different program/service, and those who received no referral. For providers, we will examine differences in their patient panel (e.g. those with CV risk factors under control at follow-up) by their engagement in the CV toolkit program. To evaluate the CV toolkit, we will use the nonrandomized stepped wedge design, a generalized mixed model coupled with an allowance for nonrandom effects, to evaluate the implementation across the providers at four sites. The intervention will be defined as “turning on” when a provider first engages in the CV toolkit (first

uses the CV template). We will model the effect of the implementation of the CV toolkit intervention on referral rates, while controlling for organizational level, provider level and patient level covariates.

**Impact-focused evaluation:** Secondary aims focus on factors that empower Women Veterans to engage in and benefit from care. We will use generalized linear mixed models (GLM) to evaluate a) cross-sectional relationships of patient activation, health-related quality of life, and care experiences at enrollment, with provider and site characteristics, adjusting for patient social and demographic characteristics; and b) prospective changes in patient activation, health-related quality of life, and care experiences from enrollment to 6-month follow-up, adjusting for patient, provider, and site characteristics. We will also construct multi-level mediation and moderation models to explore whether engagement-related factors such as patient activation, strength of treatment preferences, or the communication subscale of the CAHPS are associated with greater benefit from or satisfaction with care.

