**Power Analysis:** Our goal with the power analysis was to ascertain the number of providers who would need to “turn on” the intervention (i.e., the number of PCPs who use the CV template, as well as the minimum number of patients that would need to be exposed to the care model. Consistent with our nonrandomized stepped wedge design, the power analysis presented here is for a 3-level hierarchical linear model where patients are clustered within PCPs within sites. In the final analysis structure, patients are the Level 1 units, the timing of PCP template use/referrals represents Level 2 units, and sites are the Level 3 units. The outcome of interest for CV Toolkit is the number of referrals to services (e.g. *Gateway to Healthy Living* and other services). The outcome is binary (referred/retained vs. not), and measured at the patient level (Level 1). Treatment effect is measured at Level 2, i.e., timing of when the PCPs turn on. Parameters required for calculating power are: alpha ( $\alpha$ ) = 0.05, sample size of patients clustered within referring PCPs ( $n$ ) = at least 260 (based on prior work), the number of sites ( $K$ ) = 4, the Plausible for Retention among those with low utilization (PI) = 5% to 85%, and Effect Size Variability (ESV) = medium or 0.05. Based on the resulting power curve, we need at least 8.78 (rounded to 9) referring PCPs per site to achieve power at 0.80. Our power analyses assume that the treatment effect is linear over time, i.e. patients that are retained longer have proportionally better outcomes. While selected details of the resulting dose response curve may vary, sensitivity analyses demonstrate a reasonable approximation enabling detection of treatment effects.

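### Survey model (a) relates outcomes to site characteristics with only four sites and no small-sample method, so default Wald tests of a site characteristic would reject too often

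*Combined protocol and SAP*

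**What the plan says.** Section 5.6 (Data Analysis, paragraph on the impact-focused evaluation) sets out the survey analyses as secondary aims: "We will use generalized linear mixed models (GLM) to evaluate" two things. Model (a) concerns "cross-sectional relationships of patient activation, health-related quality of life, and care experiences at enrollment, with provider and site characteristics". Site characteristics are explanatory variables of interest there, and only patients' social and demographic features are adjusters. Model (b) concerns change from enrollment to six months, "adjusting for patient, provider, and site characteristics", so site characteristics are adjusters only.

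Section 5.1 (Veteran involvement and Characteristics) gives the size: "Our goal is to have 260 women total (minimum 65 per site across 4 sites) engaged in the project". The power paragraph of section 5.6 also has "the number of sites ( $K$ ) = 4".

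For the survey models the plan does not list the site characteristics or limit their number. It does not state the random effects, the choice of REML or ML, or a degrees-of-freedom method. It does not say that site-level results are descriptive.

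**The concern.** The information about a site characteristic lies in the differences between sites, and there are four sites. More women per site sharpen the four site means but do not add a fifth. A mixed-model fit to 260 women, read with the usual Wald z test, takes the estimated between-site variance as if it were known, although it rests on at most 2 degrees of freedom. The risk is that a chance ordering of four sites is reported as an association between, for example, activation and some feature of the clinics, with an interval that is too narrow.

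**Working it through.** **Inputs from the documents.** Sites: 4. Women: at least 65 per site, 4 x 65 = 260. Significance level: "alpha ( $\alpha$ ) = 0.05", stated for the referral power analysis only and without sidedness; two-sided is assumed here.

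**Input not in the documents.** The between-site ICC of activation, quality of life and care experiences. It is assumed to lie between 0 and 0.10. The design section describes the sites as heterogeneous, so zero is not the natural planning value, but the documents do not exclude it.

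**The plan's own figure.** None exists for these models. The only power figure, 8.78 rounded up to 9 PCPs per site, is for referrals. It cannot be reproduced, because no referral rates, effect size or ICC are given, and it does not bear on the survey models.

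**Step 1: degrees of freedom.** With q site characteristics, between-site df = 4 - 1 - q.

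- q = 1: 2 df
- q = 2: 1 df
- q = 3: 0 df; the characteristics fit the four sites exactly

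The plan uses the plural, so 2 df is the best case.

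**Step 2: what a valid test needs.** With q = 1 the reference is t on 2 df, critical value 4.303. The smallest significant correlation between the characteristic and the four site means is

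r = t / sqrt(2 + t^2) = 4.303 / sqrt(2 + 18.52) = 4.303 / 4.530 = 0.95.

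With the Wald z cut-off put into the same formula, 1.96 / sqrt(2 + 3.842) = 1.96 / 2.417 = 0.81 would pass.

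**Step 3: limiting false-positive rate of the Wald z test.** When between-site variance dominates, the REML Wald statistic follows t on 2 df but is compared with 1.96. For 2 df the two-sided tail is 1 - t / sqrt(2 + t^2), so the rate is 1 - 0.811 = 0.189. ML divides the between-site sum of squares by 4 instead of 2, so the effective cut-off is 1.96 / sqrt(2) = 1.386, and the rate is 1 - 1.386 / sqrt(2 + 1.921) = 1 - 0.700 = 0.300.

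**Step 4: rates at smaller ICCs.** Simulation of a balanced random-site model with one site characteristic of no effect, 65 women per site, 200,000 replicates per setting, and site variance truncated at zero:

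| Assumed site ICC | REML, Wald z | ML, Wald z | t on 2 df |
|---|---|---|---|
| 0 | 0.038 | 0.048 | 0.050 |
| 0.005 | 0.060 | 0.080 | 0.050 |
| 0.01 | 0.080 | 0.109 | 0.050 |
| 0.02 | 0.107 | 0.153 | 0.050 |
| 0.05 | 0.148 | 0.223 | 0.050 |
| 0.10 | 0.171 | 0.265 | 0.050 |

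Over ICC 0.01 to 0.10 the REML rate is 0.080/0.05 = 1.6 to 0.171/0.05 = 3.4 times nominal. A check with a standard mixed-model routine (REML, Wald z, 400 fits per ICC) gave 0.024, 0.083, 0.094, 0.126 and 0.156 at ICC 0, 0.01, 0.02, 0.05 and 0.10, the same pattern within simulation error. With 45 women per site the REML rate is 0.070 at ICC 0.01 and 0.134 at 0.05, so a smaller sample changes little.

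**Step 5: provider characteristics.** These are not tied to four values. At the planned 9 PCPs per site there are 4 x 9 = 36 PCPs, about 260 / 36 = 7.2 women each. With site as a fixed factor, 36 - 4 = 32 between-PCP df remain before provider characteristics are entered. At 4 PCPs per site, the low end of the site-selection criterion in section 5.1, the figure is 16 - 4 = 12. Both are workable with a small-sample method.

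**The case against.** The strongest reply is that the plan names no test. It does not commit to Wald z, and a statistician who used between-site degrees of freedom would have exactly 5% at every ICC. The ICC is assumed, and at zero the REML Wald test is slightly conservative (0.038). The analysis is secondary. All of this stands, and it makes the inflation conditional. It does not remove the problem: the stated analysis, run with ordinary mixed-model inference, gives invalid site-level tests unless site ICC is close to zero, and the valid version has almost no power.

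Several stronger readings are tempting, and the documents do not support them:

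- **That site differences will be presented as causes.** Model (a) is framed as relationships, and the mediation and moderation models as exploration.
- **That these coefficients will steer dissemination.** Sections 5.1 and 5.6 tie scale-up and spread to stakeholder feedback and the post-implementation interviews, not to site-level survey coefficients.
- **That the referral model has the same fault.** It models toolkit use "while controlling for organizational level, provider level and patient level covariates", so site-level covariates are adjusters there, not the object of a test. The same is true of survey model (b).
- **That site will be left out of the model altogether.** The false-positive rate would then be higher (0.129 at ICC 0.01, 0.483 at 0.10), but nothing in the plan says so. The multilevel structures that it does describe, for the referral model, include site.

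**Conclusion.** The point holds for the site half of model (a). Four sites give at most 2 between-site degrees of freedom, and none once three characteristics are entered. The plan neither limits the characteristics nor names a small-sample method. Under REML with Wald z, one null site characteristic would be called significant about 8% to 17% of the time at a site ICC of 0.01 to 0.10, and about 4% at ICC 0; under ML the range is about 11% to 27%. These figures assume one characteristic, equal site sizes of 65, a continuous outcome, a two-sided 5% level and the stated ICC range. The 2-df limit and the 0.95 correlation threshold need no ICC assumption. Provider characteristics in model (a) and the referral analysis are not affected.

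**What to change.** **Model (a).** Enter site as a fixed factor with three indicators. Report the four site means with intervals, and set out site characteristics beside them in a descriptive table without tests. If one site characteristic must be tested, name it in advance, use between-site degrees of freedom (t on 2 df), and label the result exploratory. Keep formal inference for provider characteristics, with a random effect for PCP and a small-sample degrees-of-freedom method such as Kenward-Roger or Satterthwaite.

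**Model (b).** The same site factor can replace the site characteristics as adjusters. It absorbs every site difference that is constant over time, measured or not.

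**Cost.** A few sentences in the analysis section; no change to data collection or sample size. The downside is that no association with a site characteristic is formally tested. With four sites that test would detect only a near-perfect alignment of the site means with the characteristic, so little is lost.

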The CV Toolkit includes four elements: (1) Patient education/activation tools, such as informational posters and fliers about women's CV risk, including information about MyHealtheVet website resources. To activate patients to discuss CV risk with their providers, we developed a CV worksheet (Appendix 6) for patients to fill out at check-in to collect information about family history of CVD, pregnancy/gestational history, and smoking status, and to help patients formulate/document any questions regarding their CV risks that they would like to discuss during their visits. The goal is to help make CV risk discussion a priority for women before they enter the exam room. (2) A CV risk assessment computerized template systematically captures CVD risk factor history and data from the medical record, and provides open fields for the provider to enter any relevant information from the patient worksheet and the clinic visit (e.g., goals and decisions). The template also includes embedded links to locate CV guideline documents. Based on feedback from clinical teams at two GLA sites, the template includes data from the current visit as well as the last three entries in the medical record (automatically generated by the template) such as weight, blood pressure, and cholesterol lab results. This enables the provider to look at trends in risk factors without having to search the chart. The information is stored as a standard outpatient note in the patient's medical record (in CPRS) and is readily accessible (and searchable) at future visits so that CV risk status will be an ongoing discussion. Referral options are also included on the template, including referral to the *Gateway to Healthy Living* program, so the template will be a shared template available for other providers to access (e.g. health coach, dietitian, specialist, etc.) to review when the patient comes for the referral. (3) Provider information and education programs as well as referral tools to internal services (e.g., women's MOVE! program, smoking cessation clinics, dieticians, health coaches, pharmacists and CV or mental health specialists as needed). (4) The *Gateway to Healthy Living* program tailored to Women Veterans is a facilitated group meeting that occurs in a structured format with personalized goal setting and identification of key services available at the local site to assist with lifestyle changes necessary for patient-targeted CV risk reduction. In addition to the structured group, it includes at least two follow up phone calls from the facilitator (typically a health coach or health promotion disease prevention specialist) for support, reinforcement of lifestyle changes, brainstorming of barriers, and steps toward goal realization.

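### Cheap improvement: the enrollment survey model names no clinical case-mix covariate, so its provider and site associations may be confounded by illness burden; show a case-mix-adjusted model beside it

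*Combined protocol and SAP*

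**What the plan says.** Section 5.6 (Data Analysis), Impact-focused evaluation, introduces this work with "Secondary aims focus on factors that empower Women Veterans to engage in and benefit from care". It then plans two generalized linear mixed models on the survey outcomes.

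- Model (a) relates activation, quality of life and care experience, measured "at enrollment, with provider and site characteristics, adjusting for patient social and demographic characteristics".
- Model (b) takes the change in the same outcomes "from enrollment to 6-month follow-up, adjusting for patient, provider, and site characteristics".

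The referral model, under Quantitative Analysis in the same section, is described as "controlling for organizational level, provider level and patient level covariates".

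Clinical information will exist in the medical record. Section 5.1 (Site Selection, CV Toolkit, and REP Implementation Phases) says "the template includes data from the current visit as well as the last three entries in the medical record", with weight, blood pressure and cholesterol as examples. The patient worksheet, which feeds the template, asks about smoking and about family and pregnancy history. On joining these data to the survey, Section 5.1 (Veteran involvement and Characteristics) says "The women will also be consented to link their responses to their medical records at the time of the survey". The same subsection says record data, including template data, stay unlinked to survey answers without that consent.

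**The concern.** Model (a) exists to estimate how patient-reported outcomes vary with provider and site characteristics. One outcome, health-related quality of life, depends directly on how ill a woman is. Women reach a provider or site by choice, geography and referral. They reach the survey because a template was activated at their visit or because they attended Gateway. Both routes can leave some providers or sites with sicker respondents.

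If illness burden runs along with a provider or site characteristic under study, and the social and demographic covariates do not carry it, part of the illness effect will appear as an association with that characteristic. Random effects for provider or site do not remove this. At stake is the interpretation of a stated secondary aim, at a point where the information needed to check it is largely being collected anyway.

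**Working it through.** **Text.** The patient adjustment in model (a) is a stated, limited list. Model (b) says "adjusting for patient, provider, and site characteristics" and lists nothing. The referral model has unlisted patient covariates, but they apply to referral rates. No other section adds a health-status term to model (a).

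**When bias arises.** Three conditions must hold together:

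1. Illness burden differs with the provider or site characteristic.
2. Illness burden is related to the outcome.
3. The social and demographic covariates do not already absorb it.

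The documents give no data on any of the three. They do say that sites are heterogeneous (Section 5.1, stepped wedge design), but not that they differ in illness burden.

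**Scale.** The plan states no power, effect size or variance for model (a), so there is no figure to reproduce. The following is an illustration.

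Inputs from the documents:
- 260 women over 4 sites.
- Alpha 0.05, given for the referral power analysis; two-sided is assumed here.
- 9 PCPs per site, the referral power target, so 4 × 9 = 36 PCPs and 260/36 = 7.22 women per PCP.

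Assumed inputs, not in the documents:
- A provider characteristic splits PCPs and women evenly (18 v 18 and 130 v 130).
- PCP intraclass correlation (ICC) is 0.02 to 0.05.
- The share of women with substantial chronic disease differs by 0 or by 10 to 30 percentage points between the two groups.
- Such disease lowers quality of life by 0.4 to 0.6 SD.
- Social and demographic covariates absorb none of this.

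Formulas:
- SE = √(4/260 × [1 + (7.22 − 1) × ICC]). ICC 0.02: √(4/260 × 1.124) = 0.132. ICC 0.05: √(4/260 × 1.311) = 0.142.
- Spurious difference = prevalence gap × effect of disease.
- Rejection rate with no true relationship: noncentral t, 36 − 2 = 34 df, noncentrality = spurious difference / SE.

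| Gap × effect | Spurious difference (SD) | Rejection, ICC 0.02 | Rejection, ICC 0.05 |
|---|---|---|---|
| no gap | 0 | 5.0% | 5.0% |
| 0.10 × 0.4 | 0.04 | 6.0% | 5.9% |
| 0.18 × 0.5 | 0.09 | about 10% | about 9% |
| 0.30 × 0.6 | 0.18 | 26.5% | 23.4% |

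**Sensitivity.**
- With 4 PCPs per site (the lower figure in the site eligibility criterion), there are 16 PCPs, 16.25 women each and 14 df. SE is 0.142 (ICC 0.02) or 0.165 (ICC 0.05), and the last row falls to 22% or 17%.
- The last row is not a ceiling. If the outcome shifts 0.5 SD per SD of illness and the groups differ by 0.5 SD of illness, the spurious difference is 0.5 × 0.5 = 0.25 SD. A normal approximation with 36 PCPs then gives 42% (ICC 0.05) to 52% (ICC 0).
- Site characteristics are not covered by this calculation. With four sites, those estimates have very few degrees of freedom.

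**The case against.** The strongest reply is that nothing in the documents shows illness burden to be aligned with any provider or site characteristic. Case-mix variation unrelated to the characteristic adds provider-level variance, which a mixed model can carry, and no bias. This stands. A reader might infer that illness differences will be reported as provider or site differences; the documents support only that they may be.

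A reader might also infer that models (a) and (b) use different patient covariates. The wording differs, but (b) lists none, and its reference to patient characteristics could be shorthand for the set just named. That inference is not established.

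A third reply is that clinical adjustment is not plainly right. Women enter at their first visit within the 15-month implementation period, which need not be their first visit ever. Prior diagnoses, BMI and smoking may reflect earlier care from the same provider, and diagnosis depends on how a provider screens and codes. Mental health diagnoses overlap with quality of life itself. If the target is the total association, adjustment could remove part of it. This also stands, and it argues against replacing the planned model, but not against showing a second one.

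Finally, clinical data are not available for everyone. Worksheet values reach the study through the template, and template data count as record data that cannot be joined to the survey without consent. Some women enter through Gateway attendance and may have no template entry. So worksheet and template values are not a fallback for women who decline linkage.

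**Conclusion.** The point holds as a cheap improvement to a secondary analysis. The stated adjustment set for model (a) leaves out clinical case mix, so its provider and site associations cannot be separated from illness burden. The size is unknown. On assumed inputs the false-positive rate for a provider characteristic is 5% with no case-mix gap, 6% with a small gap and about 27% with a large one, with higher values under more extreme assumptions. Every driver of that range is assumed.

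A reader might extend this to the evaluation of the toolkit or to a ranking of providers or sites. The documents do not support that. Model (a) is a cross-sectional association under the secondary aims, the referral model has its own covariate statement, and the plan ties no decision to model (a).

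**What to change.** In Section 5.6, Impact-focused evaluation:

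1. Keep model (a) as planned.
2. Pre-specify beside it a case-mix-adjusted model that adds diagnosed conditions (diabetes, hypertension, lipid disorder, CVD, mental health), BMI and smoking. Take these from linked record entries dated before the toolkit visit, so that what the toolkit itself uncovers is not adjusted away.
3. Name the patient covariates and use the same ones in (a) and (b).
4. Report both versions of (a). Call a provider or site association robust only if it persists after case-mix adjustment, and describe all results as associations.
5. State how missing clinical values will be handled: multiple imputation, or an analysis restricted to linked women. A missing-value indicator can leave residual confounding.

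The cost is a short paragraph of plan text, one further model per outcome and the handling of women without linkage. Pre-visit diagnoses may still carry some effect of earlier care from the same provider, which is the reason to show both models.

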#### Nonrandomized Stepped Wedge Study Design for Implementation Trials.

The CV Toolkit project will use a nonrandomized stepped wedge design, which rely on sequential roll-out to participating sites over time, while using other sites as controls until they begin implementation. Consistent with our substantial prior experience using these designs in VHA and armed with complexity theory's recognition of nonlinearity of implementation, we will use *nonrandomized* stepped wedges (rather than randomized) given their suitability for studying implementation. This design acknowledges that sites are heterogeneous, face multiple constraints, and, as a result, are ready to adopt interventions at different rates. The modified design explicitly considers the timing of implementation spread and addresses the statistical issues introduced by lack of randomization in implementation starts and processes. We will analytically compensate for the design by collecting patient-, provider-, and site-level data that may be associated with timing of the adoption of each intervention. We will include three levels in our hierarchical nonrandomized stepped wedge models: (1) patient, (2) time of intervention (i.e., when a provider starts using the intervention), and (3) site. Outcomes of interest (e.g. referrals to Gateway, other health promotion program and/or specialist) are measured for all patients at each site within the given intervention time period.

Nonrandomized stepped wedge designs make efficient use of all data available for within-site and between-site comparisons. For the within-site comparison, sites act as their own controls in an evaluation that compares sites pre- versus post-implementation. The comparison examines sites as they cross-over from control to intervention states. The between-site comparison evaluates the intervention period for a site vs. all other intervention and control periods for all sites. By having these two types of comparison, the design improves on the validity of the

evaluation of the intervention, by accounting for historical time trends that may occur outside of the intervention and for site contextual characteristics that may affect site performance.

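### Power is computed with patients clustered in PCPs, but the final model makes timing of template use the Level 2 unit and states no PCP random effect, so standard errors can be too narrow depending on how timing is coded

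*Combined protocol and SAP*

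**What the plan says.** The Power Analysis paragraph of section 5.6 gives two structures in consecutive sentences. Power is computed for a "3-level hierarchical linear model where patients are clustered within PCPs within sites". In the final analysis patients are Level 1, but "the timing of PCP template use/referrals represents Level 2 units" and "sites are the Level 3 units".

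The stepped wedge subsection of section 5.1 has the second structure: patient first, then "2) time of intervention (i.e., when a provider starts using the intervention), and (3) site".

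Timing is also the exposure. Section 5.6 states "Treatment effect is measured at Level 2, i.e., timing of when the PCPs turn on", and its Quantitative Analysis paragraph switches the intervention on "when a provider first engages in the CV toolkit". That paragraph names a generalized mixed model for referral rates "while controlling for organizational level, provider level and patient level covariates", but does not list the random effects. No section states a PCP random intercept, a PCP-by-period term, a PCP-robust variance, an intraclass correlation (ICC) or a small-sample method for four sites.

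**The concern.** Referral is something a PCP does, and the toolkit is switched on PCP by PCP. Section 5.1 (Veteran involvement) says that referral data cover all women seen by the study providers over the study period, so each PCP contributes many women over many months. PCPs who differ in referral habit make their own patients alike. The model needs a term for that. Provider-level covariates explain part of the difference between PCPs, but do not replace a random effect for the rest.

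With timing in the Level 2 slot, the treatment variable stands where the cluster should be. Depending on how an analyst codes it, PCPs may keep their own unit, be merged with colleagues who start in the same period, or have no unit at all. At stake is the false-positive rate of the test of the toolkit effect on referrals, and the freedom to choose among these models after the data are seen.

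**Working it through.** **1. The plan's own figure.** The 8.78 PCPs per site for power 0.80 cannot be rebuilt, because no effect size, ICC or number of periods is given. A multisite cluster formula was tried, with noncentrality = K·d² / (ESV + 4(ρ + (1−ρ)/n)/J), K = 4, J = 8.78, n from 260/36 = 7.2 to 260 per PCP, and ρ from 0.01 to 0.30. It returns 80% power for standardized effects of 0.50 to 1.02 (random sites) or 0.12 to 0.62 (fixed sites). So the power statement does not fix the size of PCP clustering, and a range must be assumed.

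**2. Assumed inputs.**
- 4 sites (section 5.6).
- 6 PCPs per site (assumption: midpoint of the 4 to 8 in the site selection criteria of section 5.1).
- 25 women per PCP-quarter, two control quarters, first use spread over five quarters, 15% of PCPs never starting (assumptions).
- PCP ICC 0.02, 0.05, 0.10 and 0.22, with 80% of PCP variance stable and 20% varying by period (assumptions).
- Site and calendar-quarter terms in every model; linear scale.

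**3. Formula.** Let R = true variance / reported variance of the toolkit coefficient. A nominal 5% test then rejects with probability 2Φ(−1.96/√R).

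With no Level 2 random term, averaged over 60 random roll-outs:
- ICC 0.02: R = 2.2, 1.96/√2.2 = 1.32, rejection about 18% to 19%
- ICC 0.05: R = 3.9, 1.96/√3.9 = 0.99, rejection 32%
- ICC 0.10: R = 6.9, 1.96/√6.9 = 0.75, rejection 46%
- ICC 0.22: R = 14, 1.96/√14 = 0.52, rejection 60%

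**4. Readings compared.** All four models on the same layout, with a smaller set of roll-outs for the first three rows:

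| Level 2 random term | ICC 0.02 | 0.05 | 0.10 | 0.22 |
|---|---|---|---|---|
| None | 19% | 36% | 46% | 63% |
| Start cohort within site | 6% | 8% | 11% | 18% |
| PCP intercept only | 6% | 8% | 11% | 19% |
| PCP plus PCP-by-period | 5% | 5% | 5% | 5% |

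Across repeat calculations, the start-cohort reading spans about 6% to 20%. Timing as an on/off or site-period unit, or with no random term, spans about 13% to 65%.

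Inverting the formula, √R = 1.96/z, where z is the two-sided normal critical value for the rejection rate. For 6% and 20%, z = 1.88 and 1.28, so √R = 1.04 and 1.53. For 13% and 65%, z = 1.51 and 0.454, so √R = 1.30 and 4.32. The reported standard error is too small by those factors.

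**5. Sensitivity.** With 7 women per PCP-quarter, the model with no Level 2 term rejects 9% to 36% of the time and the start-cohort model 5% to 8%. If all PCP variance is stable over time, the start-cohort model rejects 4% to 5%.

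**6. A different layout.** Take 4 sites of 9 PCPs over 10 quarters, three PCPs sharing each start, no period-varying PCP component, and PCP ICC 0.02 to 0.30. The ratio of true to reported standard error is:
- 1.00 when each PCP has its own start date.
- 0.36 to 1.00 with shared timing units and a common effect: correct or too wide.
- 0.98 to 1.00 with no Level 2 term when every PCP switches.
- 1.07 to 2.95 with no Level 2 term when three of nine never switch (rejection about 7% to 51%).
- If the effect varies by site with variance 0.05 and this is not modelled, 1.04 to 2.37 with timing at Level 2 and 1.13 to 3.30 with PCP at Level 2. A site-level random treatment effect brings this to 1.00 when the variances are known.

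**The case against.** The strongest reply is that the label is loose and the model is sound. Timing is defined by each provider's own first use, and the preceding sentence of section 5.6 has "patients are clustered within PCPs within sites". If dates are distinct, a unit indexed by start date is that PCP. A generalized mixed model may also carry a PCP effect that is simply not listed. This stands in part: under that reading the PCP intercept is kept. But the plan does not say that dates must be distinct, at what resolution timing is recorded, or which unit holds a PCP who never starts. With 6 PCPs and five start quarters, at least two share a quarter whenever all six start.

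A second reply is that swapping timing for PCP changes little. This also stands for the start-cohort reading, where the second and third rows of the table are nearly equal. The remaining inflation comes from the assumed period-to-period PCP variance. It shows that renaming Level 2 is not a sufficient repair.

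Stronger readings are tempting, but the documents do not support them:
- A reader might infer that PCP clustering is lost and the intervals are far too narrow. That holds only for some codings. The 18% to 60% figures belong to a model with no Level 2 random term, whereas the plan describes three levels, and in some layouts the intervals are too wide.
- A reader might take ICC 0.22 from the plan's 5% to 85% range. As a 95% range across PCPs it gives a logit SD of (1.735 + 2.944)/3.92 = 1.19 and a probability-scale ICC near 0.22. But the plan ties that range to retention among low users, not to differences between PCPs in referral.
- A reader might apply a critical t of 4.30 (2 degrees of freedom after one organizational covariate) to the toolkit effect. That value concerns a site-level covariate. The toolkit effect is placed at Level 2 and has a within-site comparison, so site degrees of freedom do not govern its test if the effect is common across sites.

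**Conclusion.** The inconsistency is on the page: PCP is the cluster for power, timing is the Level 2 unit for analysis, and timing is also the treatment. Since no PCP random effect or PCP-robust variance is stated, the plan admits models with very different error rates. Under the assumptions listed, the false-positive rate is about 6% to 20% if timing is a start-cohort intercept, and about 13% to 65% if it is an on/off or site-period unit or has no random term. PCP plus PCP-by-period holds 5% throughout. If every PCP has a unique start date, the PCP intercept is preserved, though the period-to-period component is still missing.

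The sizes rest on an assumed layout, assumed ICCs and a linear approximation to a binary outcome. The upper ends rely on ICC 0.22, which the documents do not establish. The handling of four sites is a secondary matter: a site variance rests on 3 degrees of freedom and will be imprecise, and a treatment effect that differs by site needs its own term whichever Level 2 unit is used.

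**What to change.** In the stepped wedge subsection of section 5.1 and the Power Analysis paragraph of section 5.6, list the random effects and make the two sections agree:

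1. Make PCP the Level 2 random intercept.
2. Add a PCP-by-period term, or use PCP-robust standard errors with a small-sample correction (4 × 6 = 24 PCPs in the layout above, 4 × 9 = 36 at the plan's own target). A PCP intercept alone is not enough.
3. Enter treatment as a time-varying PCP-level fixed effect, either on/off or time since first use, with calendar-period terms. State how PCPs who never use the template are coded.
4. Secondary: state how site is handled, for example as four fixed indicators, and whether the effect may vary by site.

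This should be settled before the referral data are analysed. It needs SAP wording and model code, and no new data. The price is wider intervals and, if site is fixed, organizational covariates that are no longer estimated in this model.
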